|---|-------------------|-------------|----------------|-------|-----------|----------------|--------------|-------------|--------|--------|------------------|
| | Visit 1 | Visit 2 | | | | Visit 3 | | Visit 4 | | | Visit 5 |
| Assessment | Day -28 to Day -2 | Day -1 | Day 1 | Day 2 | Day 3 & 4 | Day 5 | Day 6, 7 & 8 | Day 9 | Day 10 | Day 11 | Day 19 (±2 days) |
| Informed Consent | X | | | | | | | | | | |
| Inclusion/exclusion criteria | X | | X ¹ | | | | | | | | |
| Weight/height/BMI | X | | | | | | | | | | X ² |
| Medical/surgical history | X | | | | | | | | | | |
| Demographics | X | | | | | | | | | | |
| HIV, hepatitis B and C | X | | | | | | | | | | |
| Urine Drug Screen ³ | X | X | | | | | | X | | | X |
| Alcohol breath test | X | X | | | | | | X | | | X |
| Pregnancy Test ⁴ | X | X | | | | | | X | | | X |
| Physical Examination | X | | | | | | | | | | X |
| Clinical Laboratory Profile ⁵ | X | | | | | | | | | | X |
| Vital signs | X | | | | | | | | | | X |
| 12-lead paper ECG | X | | | | | | | | | | X |
| Celecoxib administration BID ⁶ | | | X | X | X | X | X | X | X | | |
| Blood sampling for WBA ⁷ | | | X | X | | | | | X | X | |
| Blood sampling for ADMA analysis ⁷ | | | X | X | | | | | X | X | |
| Blood sampling for future biomarker analyses ⁷ | | | X | X | | | | | X | X | |
| Urine collection ⁸ | | X | X | X | | | | | X | X | |
| Meals ⁹ | | X | X | X | | | | X | X | X | |
| Baseline symptoms | X | X | | | | | | | | | |
| AEs and SAEs ¹⁰ | | | | | | | | | | | X |
| Prior and concomitant medications | | | | | | | | | | | X |

1. Confirmation of eligibility prior to randomisation. Day -1 or Day 1.
2. Weight only.
3. Random drug screening test may also be performed at the discretion of the investigator.
4. WOCBP only. Screening: plasma/serum tests, other visits: urine test.
5. Clinical chemistry, haematology, coagulation, urinalysis (dip-stick), see Section 11.3.6.
6. To be taken each morning and evening at the same time (± 1 h). Self-administration at home from the evening of Day 2 to the evening of Day 8.
7. Blood samples for WBA, ADMA and future biomarker analyses are drawn 0 h (within 60 min pre-dose) and 2 h, 8 h and 24 h post administration of celecoxib on Day 1 and Day 10 (24 h samples taken pre-dose on Day 2 and 24 h post last dose on Day 11, respectively).
8. Urine for PD analysis will be collected at the following intervals: 0 to 6 h, 6 to 12 h and 12-24 h post administration of celecoxib on Day 1 and Day 10. In addition, baseline urine is collected -24 h to -12 h and -12 h to 0 h prior to the first celecoxib administration on Day -1/Day 1.
9. Breakfast, lunch, snack, dinner and evening snack. Breakfast only on Day 2 and 11.
10. From administration of IMP.

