6.7 Risk/benefit assessment

Part I, II and III

The healthy volunteers in Part I and II (single ascending dose [SAD] and multiple ascending dose [MAD], respectively) in this study will, except for thorough health examinations, have no medical benefit from participation and their safety and wellbeing are of outmost importance. The study involves the first administration of GS-248 to humans, and there are no previous data on the effects of the drug in humans. It is therefore difficult to make predictions about possible adverse drug reactions (ADRs).

Pronounced and serious effects on the liver and biliary system were noted in dogs at the highest dose in the 28-day toxicity study. However, no findings that were considered to constitute an adverse effect were noted at the intermediate dose level, primarily based on the total lack of treatment-related histopathological findings at this dose level, and the NOAEL in this study was therefore set at 20 mg/kg.

The liver biomarkers will be closely monitored during the present study, providing the possibility to stop dosing in individuals with signs on emerging liver toxicity. The medical monitor will continuously review individual subjects to decide if dosing should be discontinued. An internal safety review committee (iSRC) will review both individual subjects and trends between dosing groups as recommended in the U.S. Food and Drug Administration (FDA) Guidance on Drug-Induced Liver Injury [25] to decide if dosing should be continued, and in that case at which dose level, see Section 9.7.3. Stopping of further dosing or adjustments from the intended dosing scheme can be considered also if the stopping rules recommended in the Guidance are not fulfilled.

Mild increases in serum cholesterol levels have been noted in both rats and dogs at all dose levels included in the 28-day toxicity studies. However, these changes were of a low degree and were therefore not considered to be adverse effects. The likelihood of any clinically relevant increases in serum cholesterol in the present study is low, but serum cholesterol will be monitored throughout the study in order to discern any evolving effects.

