Before initiating a new cohort, all subjects in the previous cohort must have been treated and 48 h safety, tolerability and PK data for all treated subjects must have been evaluated by the iSRC, see Section 8.3.8. Once Day 3 safety, tolerability and PK data for the last subject in each cohort has been collected, there will be at least 1 week between dose escalations.

Each subject is expected to participate in the study for approximately 36 days including a 28-day screening period.

The schedule of events for Part I is shown in Table 8.1-1 and detailed for Visit 2 in Table 8.1-2. Study assessments are described in Section 11.

Safety assessments include: AE reporting, 12-lead ECG monitoring, vital signs (blood pressure and pulse), body temperature, physical examination, use of concomitant medications and blood sampling for haematology, clinical chemistry and coagulation parameters, see Section 11.3.

PK assessments include: blood sampling for bioanalysis and subsequent determination of PK parameters, see Section 11.4.

Exploratory assessments include: blood sampling for analysis of mPGES-1 activity (PGE₂ levels) in an *ex vivo* WBA, for future biomarker analysis (from cohort 3 and onwards) and for future exploratory analysis of metabolites, see Section 11.5.

Table 8.1-1 Schedule of events Part I (SAD)

| | Screening | Residential period | | | | End-of-study |
|--|--------------------------------|-------------------------------|--------------------|-----------------|-----------------|-----------------|
| Visit | Visit 1 | Visit 2 ¹ | | | | Visit 3 |
| Assessment | Day -28 to Day -1 ² | Admission Day -1 ² | Day 1 | Day 2 | Day 3 | Day 8 (±2 days) |
| Informed Consent | X | | | | | |
| Inclusion/exclusion criteria | X | | X ³ | | | |
| Weight/height/BMI | X | | | | | X ⁴ |
| Medical/surgical history | X | | | | | |
| Demographics | X | | | | | |
| HIV, hepatitis B and C | X | | | | | |
| Urine Drug Screen ⁵ | X | X | | | | X |
| Alcohol breath test | X | X | | | | X |
| Pregnancy Test (WOCBP) ⁶ | X | X | | | | X |
| Physical Examination | X | | X ^{7, 8} | | | X |
| Clinical Laboratory Profile ⁹ | X | X | | | X | X |
| Vital signs ¹⁰ | X | X | X ¹¹ | X | X | X |
| Body temperature | | | X ⁸ | | | |
| 12-lead ECG | X | | X ^{8, 11} | X | X | X |
| Telemetry | | | X ¹² | | | |
| Randomisation | | | X | | | |
| IMP administration ¹³ | | | X | | | |
| PK blood sampling ¹⁴ | | | X ¹¹ | X ¹¹ | X ¹¹ | |
| Blood sampling for WBA ¹⁵ | | | X ¹⁵ | X ¹⁵ | | |

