Before initiating a new cohort, all subjects in the previous cohort must have been treated and 11 days safety, tolerability and PK data (i.e. data up to and including 24 h post last dose) for all treated subjects must have been evaluated by the iSRC, see Section 8.3.8. Once Day 11 safety, tolerability and PK data for the last subject in each cohort has been collected, there will be at least 1 week between dose escalations.

Each subject is expected to participate in the study for approximately 47 days including a 27-day screening period.

The schedule of events for Part II is shown in Table 8.1-3 and is detailed for Visit 2 and Visit 9 in Table 8.1-4. Study assessments are described in Section 11.

Safety assessments include: AE reporting, 12-lead ECG monitoring, vital signs (blood pressure and pulse), body temperature, physical examination, use of concomitant medications and blood sampling for haematology, clinical chemistry and coagulation parameters, see Section 11.3.

PK assessments include: blood sampling for bioanalysis and subsequent determination of GS-248 PK parameters, see Section 11.4.

Exploratory assessments include: blood sampling for analysis of mPGES-1 activity (PGE₂ levels) in an *ex vivo* WBA, blood and urine sampling for analysis of ADMA in plasma and AA metabolites in urine, blood and urine sampling for future exploratory analysis of GS-248 metabolites and for future exploratory biomarker analyses, see Section 11.5.

Table 8.1-3 Schedule of events Part II (MAD)

| | Screening | Residential period | | | | Daily visits | Residential period | | | | End-of-study |
|--|-------------------|----------------------|--------------------|-----------------|-------|-----------------|----------------------|---------------------|-----------------|----------------|----------------|
| Visit | Visit 1 | Visit 2 ¹ | | | | Visit 3 to 7 | Visit 8 ¹ | | | | Visit 9 |
| Assessment | Day -28 to Day -2 | Admission Day -1 | Day 1 | Day 2 | Day 3 | Day 4 to 8 | Admission Day 9 | Day 10 | Day 11 | Day 12 | Day 19 (±2) |
| Informed Consent | X | | | | | | | | | | |
| Inclusion/exclusion criteria | X | | X ² | | | | | | | | |
| Weight/height/BMI | X | | | | | | | | | | X ³ |
| Medical/surgical history | X | | | | | | | | | | |
| Demographics | X | | | | | | | | | | |
| HIV, hepatitis B and C | X | | | | | | | | | | |
| Urine Drug Screen ⁴ | X | X | | | | | X | | | | X |
| Alcohol breath test | X | X | | | | | X | | | | X |

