9. Clinical chemistry only on Day 2 and Day 6. Approximately 8 h post-dose on Day 2 and pre-dose on Day 6. No clinical laboratory sampling on Day 4, 5, 7 and 8.
10. Blood pressure and pulse, see Section 11.3.3.
11. For timing of assessments, refer to Table 8.1-4.
12. Once daily administration of IMP. On Day 1 and Day 10, administration under fasting conditions, i.e. fasting for 10 h before IMP administration until 4 h post administration. On Days 2 to 9, administration prior to breakfast at the same time each morning (±1 h).
13. Includes sampling for future exploratory analyses of potential GS-248 metabolites.
14. Pre-dose PK samples on Day 8, 9 and 10 must be taken within 5 minutes before dose.
15. Future exploratory analyses of biomarkers e.g. inflammatory biomarkers.
16. Urine for analysis of AA metabolites and for future analysis of GS-248 metabolites and biomarkers will be collected at the following intervals: 0 to 6 h, 6 to 12 h and 12-24 h post administration of study drug on Day 1 and Day 10. In addition, baseline urine is collected -24 h to -12 h and -12 h to 0 h prior to the first IMP administration on Day -1/Day 1.
17. Breakfast, lunch, snack, dinner and evening snack. Standardised meals during 24 h after dose on Day 1 and Day 10. For timing of meals, refer to Table 8.1-4. No breakfast on Day 1 and Day 10. Breakfast only on Day 3 and Day 12.
18. From administration of IMP.

Table 8.1-4 Detailed schedule of events for Visit 2 and Visit 8, Part II (MAD)

| Assessment/time-point | Day -1 | Day 9 | Day 1/Day 10 | | | | | | | | | | | Day 2/Day 11 | | Day 3/Day 12 |
|--|-----------------|-----------------|--------------------|-------|------|----|----|----|--------------------|----|-----|-----|-----------------|-----------------|-----------------|--------------|
| | Admission | Pre-dose | 0 | 0.25h | 0.5h | 1h | 2h | 4h | 6h | 8h | 12h | 16h | 24h | 36h | 48 h | |
| Inclusion/exclusion criteria | | | X ¹ | | | | | | | | | | | | | |
| Pregnancy test (WOCBP) | X | X | | | | | | | | | | | | | | |
| Urine drug screen | X | X | | | | | | | | | | | | | | |
| Alcohol breath test | X | X | | | | | | | | | | | | | | |
| Physical examination | | | X ^{1,2} | | | | | | | | | | | | X ³ | |
| Clinical laboratory profile | X | X | | | | | | | | | | | X ⁵ | | X | |
| Vital signs ⁶ | X | X | X | | | | X | X | X | X | X | X | X | X | X | |
| Body temperature | | | X ⁴ | | | | | | | | | | | | | |
| 12-lead ECG | | | X ⁴ | | | | | X | | | X | | X ⁷ | | X | |

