| Randomisation | | | X ⁸ | | | | | | | | | | | | | |
| IMP administration | | X | | X | | | | | | | | | X ⁹ | | X ⁹ | |
| PK blood sampling | | X ¹¹ | X ^{10,11} | | X | X | X | X | X | X | X | X | X | X ¹² | X ¹³ | |
| Blood sampling for GS-248 MIST ¹⁴ | | | X ¹¹ | | X | X | X | X | X | X | X | X | X ¹² | | | |
| Blood sampling for WBA | | | X ¹⁰ | | | | | X | | | X | | X | | | |
| Blood sampling for ADMA analysis | | | X ¹⁰ | | | | | X | | | X | | X | | | |
| Blood sampling for future biomarker analyses | | | X ¹⁰ | | | | | X | | | X | | X | | | |
| Urine collection ¹⁵ | X | | | | | | | X | | | X | | X | | | |
| Breakfast ¹⁶ | | X | | | | | | | | | | | X | | X | |
| Meals | X ¹⁷ | X ¹⁷ | | | | | | | X ^{17,18} | | | | X ¹⁷ | | X ¹⁷ | |
| Baseline symptoms | X | | X | | | | | | | | | | | | | |
| AEs and SAEs | | | | | | | | | | | X | | | | | |
| Prior and concomitant medications | | | | | | | | | X | | | | | | | |

1. Day -1 or pre-dose Day 1 prior to randomisation. Not Day 10.
2. Short version of physical examination.
3. Physical examination Day 12, not Day 3.
4. Day -1/Day 9 or pre-dose Day 1/Day 10
5. Day 2; clinical chemistry only. Approximately 8 h post-dose. Not Day 11.
6. Day 1 at time points indicated, Day 2, Day 3 and Day 10 (approximately 2 h post-dose only) and Day 12 prior to departure. Not Day 11.
7. ECG on Day 2, not Day 11.
8. Randomisation on Day 1.
9. IMP administration on Day 2 and Day 3, not Day 11 or Day 12.
10. Pre-dose sample on Day 1 should be taken within 60 minutes prior to dose.
11. Pre-dose samples on Day 8, 9 and 10 must be taken within 5 minutes before dose.
12. The 24 h PK sample is taken pre-dose Day 2 or 24 h post last dose on Day 11 within 10 minutes of the of the nominal time for the dosage interval. For details regarding time windows for PK sampling on Days 2, 8, 9 and 10, refer to Section 11.4.1.
13. 48 h after last dose on Day 12. Not Day 3.
14. Day 1 and Day 10 during 24 h in association with PK sampling. Includes sampling for future exploratory analyses of potential GS-248 metabolites.
15. Urine for analysis of AA metabolites and for future analysis of GS-248 metabolites and biomarkers will be collected at the following intervals: 0 to 6 h, 6 to 12 h and 12-24 h post administration of study drug on Day 1 and Day 10. In addition, baseline urine is collected -24 h to -12 h and -12 h to 0 h prior to the first IMP administration on Day -1/Day 1.

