A rolling review of emerging safety data will be performed throughout the study taking into account any AEs (in particular moderate AEs assessed as at least possibly related to the IMP administration), the number of subjects in whom they occur, concurrency of more than one event within the same subject and any trends. Changes from baseline measurements will also be considered and not just absolute cut-off based on upper- or lower limits of normal that might apply for healthy volunteers.

Trends or safety signals described above, which are not necessarily covered by the stopping criteria in Table 8.3-4 may warrant the scheduling of ad hoc iSRC meetings after which the iSRC will make recommendations to sponsor on e.g. whether to terminate the study or to stop dosing in individual subjects or a certain cohort.

Additional study specific withdrawal criteria are summarised in Section 9.7.

Table 8.3-4 Dose escalation and stopping rules, Part I and Part II

| Stop criterion | Action taken |
|---|---|
| At individual and dose group level | |
| If no subject has an SAE considered at least possibly related to the IMP administration, i.e. a serious adverse drug reaction (SADR) | Escalate to the next higher dose level. |
| If 1 subject on active treatment has an SAE assessed as at least possibly related to IMP administration | 
 1. Stop dosing of subject with a potential SADR. Withdrawal of subject. 2. Unblinding of subject with potential SADR. Only voting members of the iSRC will be unblinded. 3. Evaluation by iSRC. The iSRC makes recommendation to Sponsor. 4. Sponsor decides how to proceed: Subject met stop criterion: stop further dosing at this dose level for all subjects. Sponsor decides if the study will be terminated or if dosing will commence at a lower dose level or at an intermediate dose level. |

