Before initiating a new cohort, all subjects in the previous cohort must have been treated and safety, tolerability and PK data (at least 48 h data in Part I [SAD] and data up until and including 24 h post last dose in Part II [MAD]) for all treated subjects must have been evaluated by the iSRC.

If GS-248 is considered safe and tolerable, a written recommendation on the next dose level based on the predicted exposure will be provided to the Sponsor. Likewise, the iSRC will recommend dose levels for Part II and III, respectively, based on review of data from earlier cohorts/study parts.

Details regarding timing of iSRC review and the data to be reviewed will be provided in a separate iSRC charter. Based on emerging safety and PK information, the amount of safety and PK data to be reviewed after a completed cohort might be adjusted.

The voting members of the iSRC will consist of the Principal Investigator and the Sponsor's medically responsible person or delegate. In addition, the study clinical research manager (CRM), the study pharmacokineticist, additional Sponsor representatives and further internal or external experts will be invited and consulted as appropriate.

An adaptive dosing strategy will be applied to allow for a flexible and safe dose escalation. The planned dose escalation is outlined in Section 8.3.2 and Section 8.3.3. The actual doses given in each cohort will be guided by the iSRC recommendations based on available safety, tolerability and PK data. Every dose step is thus adjustable and the recommendation to the Sponsor may be to continue with a higher or lower dose than the intended dose, repeat the same dose level, continue with an intermediate dose level or to stop dosing.

The recommendation of the iSRC on the next dose level will be taken in consensus between the iSRC members and documented as appropriate. In case there is disagreement between the 2 voting members, the most conservative approach will be recommended. It is not acceptable to repeat a dose level where any of the dose escalation stopping rules have been met.

In Part I and Part II, 2 or 1 additional cohort(s), respectively, may be added as needed to test additional doses or dosing schemes, repeat the dose given in a previous cohort, to establish the target dose for Part III and subsequent studies and/or to reach steady state. In Part III, 1 additional cohort (10 patients) may be added.

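### The minimum data set for Part II escalation closes on Day 11, so its last liver value is Day 9, before the tenth dose; the scheduled Day 12 profile falls one day outside it

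*Protocol*

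**What the plan says.** Protocol Section 8.1.2 makes escalation in Part II conditional on iSRC evaluation of "11 days safety, tolerability and PK data (i.e. data up to and including 24 h post last dose) for all treated subjects". Section 8.3.8 gives the same limit, "data up until and including 24 h post last dose in Part II [MAD", and the synopsis carries it too. After Day 11 data have been collected from the last subject, "there will be at least 1 week between dose escalations".

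Table 8.1-3 places the clinical laboratory profile, after first dosing, on Days 2, 3, 6, 9, 12 and 19, with Days 2 and 6 limited to chemistry. The Day 10 and Day 11 cells are blank. Footnote 9 adds "No clinical laboratory sampling on Day 4, 5, 7 and 8". In Table 8.1-4 one column serves both Day 2 and Day 11, and footnote 5 settles which day applies: "Day 2; clinical chemistry only. Approximately 8 h post-dose. Not Day 11".

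For Part I, Section 8.1.1 requires that "48 h safety, tolerability and PK data for all treated subjects must have been evaluated by the iSRC". Tables 8.1-1 and 8.1-2 put a laboratory profile at 48 h, on Day 3.

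On liver safety, Section 6.7 has the iSRC look at individual subjects and at trends between dose groups "to decide if dosing should be continued, and in that case at which dose level, see Section 9.7.3". Section 8.3.7 states: "A rolling review of emerging safety data will be performed throughout the study".

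**The concern.** Section 6.4 identifies liver and biliary toxicity in dogs as the finding that limits human exposure. It came with repeated dosing, and GS-248 accumulated over treatment days in that species. Part II is where repeated dosing in humans is first tested, so a liver value taken after the full ten-dose course bears directly on whether to take the next step, which Section 8.3.3 sets at about three-fold for the second and third cohorts.

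The schedule provides that value on Day 12, but the data that must be reviewed stop on Day 11. Read literally, the escalation condition can be met with no liver result after the tenth dose. Table 8.3-4 has no row for liver chemistry, so a symptom-free rise first seen on Day 12 would not by itself trip an escalation rule unless it was judged clinically significant and reported as an adverse event of sufficient grade. Because Part I is aligned with its own post-dose profile, the Part II cut-off looks more like a slip than a choice.

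**Working it through.** The plan gives no figure to reproduce. The check sets the review window against the sampling schedule.

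**Inputs.** Tenth dose on Day 10; package through 24 h after it; at least 1 week after Day 11 collection; at most 4 subjects dosed per day (all Section 8.1.2). Chemistry on Days 2, 3, 6, 9, 12 and 19 (Tables 8.1-3 and 8.1-4). Cohorts of 6 GS-248 and 2 placebo; three cohorts as run, at 20, 60 and 180 mg (SAP Section 3.4).

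**Window against schedule**

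| | Part I | Part II |
|---|---|---|
| Package closes | 48 h after dose, Day 3 | Day 10 + 1 = Day 11 |
| Post-dose chemistry inside the package | Day 3 | Days 2, 3, 6, 9 |
| Chemistry after the final dose, inside the package | 1 | 0 |
| First chemistry after the final dose | Day 3, inside | Day 12, outside |

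**Distances in Part II**
- Day 9 to the tenth dose: 10 − 9 = 1 day.
- Day 9 to the cut-off: 11 − 9 = 2 days.
- Cut-off to the next scheduled profile: 12 − 11 = 1 day.
- The Day 9 sampling time is not stated. Drawn before the morning dose, it follows 8 doses and leaves 10 − 8 = 2 without a later required value. Drawn at evening admission, it follows 9 and leaves 10 − 9 = 1.

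**Time available.** Counting the week from Day 11 collection, the earliest next cohort is 11 + 7 = Day 18 of the last-dosed subject. Day 12 falls 18 − 12 = 6 days before that.

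**Subjects affected at the cut-off.** Eight subjects at no more than 4 per day need at least 8 / 4 = 2 dosing days. When the last subject reaches Day 11, at most 4 of the 8 are on Day 11 and at least 4 are at Day 12 or later.

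**Decisions affected.** Four planned cohorts give 4 − 1 = 3 escalations. As run there were 3 − 1 = 2, with steps of 60 / 20 = 3 and 180 / 60 = 3. The two lower cohorts behind those decisions hold 2 × 6 = 12 active and 2 × 2 = 4 placebo subjects in all. By the count above, at most 4 per cohort would lack a drawn Day 12 sample at the moment the package closes.

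The documents give no probability of a liver enzyme rise, so none is assumed.

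**The case against.** The strongest reply is that the iSRC will have the Day 12 result in practice. Section 8.3.3 gives it access to all safety, tolerability and PK data. Section 6.7 adds continuous review of individual subjects by the medical monitor and iSRC review of liver trends. Section 8.3.7 allows ad hoc iSRC meetings on signals outside Table 8.3-4. Section 8.3.8 leaves the data to be reviewed to a separate charter and allows the amount to be adjusted. With six days in hand and at least half the cohort already at Day 12, someone would have to decide without a result that had been or was about to be drawn, and nobody would have to act on it before dosing. This stands as to likelihood. It does not change the text: each provision permits sight of Day 12, and none requires it.

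A second reply is pharmacological. Section 8.3.8 predicts a human half-life of 2 to 13 h. At 13 h with 24 h dosing, accumulation is 1 / (1 − 2^(−24/13)) = 1 / (1 − 0.278) ≈ 1.4-fold, and five half-lives take 5 × 13 = 65 h. The Day 9 sample, at least 8 × 24 = 192 h after the first dose, is then 192 / 13 ≈ 15 half-lives in, so the tenth dose should add little to exposure. The dog marker rises at the no-adverse-effect dose came mainly in the first two weeks, and neither Day 9 nor Day 12 covers that period in full. This also stands and lowers the stakes, although the half-life is a prediction from animals and does not exclude injury that appears late.

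Third, exposure is capped independently. Predicted Part II exposure may not exceed that already evaluated in Part I, and one subject above the AUC or Cmax limit triggers iSRC evaluation. This is a real safeguard, but the Part I exposure is single-dose.

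A reader might infer from Table 8.3-4 that liver findings cannot stop escalation. The documents do not support that. Section 9.7.3 has individual liver stopping criteria, and clinically significant laboratory values are adverse events that can meet the severity and seriousness rules.

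**Conclusion.** The point holds as a gap in the stated minimum. The required Part II package contains four on-treatment chemistry samples and none after the tenth dose, and it omits the protocol's own post-course profile by one day. Its practical weight is modest: one or two of ten doses lack a later required value, at most 4 of 8 subjects per cohort are short of Day 12 when the package closes, and there are several routes by which the iSRC can see the result. It is still worth changing, because the missing value concerns the toxicity that sets the exposure limit and the change costs almost nothing.

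Two stronger readings should be resisted. A reader might infer that cohorts were escalated without post-course liver data. Nothing in the documents shows what the iSRC had before it at either escalation. A reader might also infer that the four-week liver monitoring in Section 9.7.3 runs past the last visit. In its natural reading, that monitoring is a condition for continuing treatment, which ends on Day 10, so no shortfall follows.

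The verdict assumes that the iSRC charter, which was not provided, does not already require Day 12 data. If it does, the remaining issue is that the protocol and the charter should agree. The Day 18 figure assumes that the one-week wait runs from Day 11 collection in the last subject.

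**What to change.** In Protocol Sections 8.1.2 and 8.3.8 and the matching synopsis sentence, define the minimum Part II package as data up to and including 48 h after the last dose (Day 12), and name the Day 12 clinical chemistry for all treated subjects as part of it. Align the iSRC charter if it differs.

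The cost is wording, plus a package that closes one day later. No sample is added, because the Day 12 profile is already scheduled. The earliest next cohort stays at Day 18 if the one-week wait continues to run from Day 11.
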